6.1.2. Overview of CBL-514

CBL-514 Injection (CBL-514), is a new injection for lipolysis product developed by Caliway Biopharmaceuticals Co., Ltd. The product is supplied with 20 mL in a glass vial with a stopper. Each mL of CBL-514 contains 5 mg the drug substance, the CBL-514 Powder, with [REDACTED] serving as the active pharmaceutical ingredients. CBL-514 is compatible to use with needle and syringe for subcutaneous injection.

CBL-514 has shown promising efficacy and safety profiles in prior research in *in vitro* and animal models for the proposed indication in promoting adipose cell apoptosis.

6.2. Summary of Nonclinical and Clinical Studies

6.2.1. Nonclinical Studies

CBL-514 has undergone an extensive nonclinical safety and efficacy evaluation. These nonclinical studies conducted for CBL-514 are described in detail in the CBL-514 IB.

The mechanism of action of CBL-514 is to trigger adipocyte apoptosis by inhibition of DYRK1b, thereby increasing the expression of Caspase-3 and Bax/Bcl-2 ratio, which are apoptosis biomarkers. Our previous nonclinical study results demonstrated that CBL-514 induced cell death of adipocyte through apoptosis mechanism and reduced the subcutaneous fat in treatment area.

[REDACTED]

[REDACTED]

6.2.2. Clinical Studies

The safety and tolerability of injection lipolysis with CBL-514, PK profile of and preliminary efficacy of 4 doses of CBL-514 in reducing abdominal subcutaneous fat at the target area was evaluated in a first-in-human, placebo-controlled, double-blind, Phase 1/2a study (CBL-16001) in Australia. In the Phase 1 component of CBL-16001, CBL-514 was administered in human for the assessment of safety and tolerability. The treatment was a SAD design in which 9 proposed dosing cohorts were involved (Cohorts 1 to 9). In 9 sequential cohorts, CBL-514 dose levels were 2 mg, 10 mg, 20 mg, 40 mg, 40 mg, 80 mg, 160 mg, 240 mg, and 320 mg per subject. For Cohorts 1 to 5, both CBL-514 and placebo groups were administered on each side of abdomen in a blinded manner to evaluate the possible AEs attributed to the components of CBL-514. For Cohorts 6 to 9, only CBL-514 was dosed in subjects.

Overall, Phase 1 results in physical examination, vital signs, ECG, and laboratory tests, including biochemistry, hematology, coagulation, and urinalysis, all showed favorable profiles for the safety of CBL-514. While there was no systemic TEAE from CBL-514, the most frequent TEAEs were ISRs.

[REDACTED]

[REDACTED]

In the Phase 1 component of CBL-16001, CBL-514 was well tolerated through the ascending dose escalation scheme from 2 mg to 320 mg.

6.3. Rationale for the Study

To date, the nonclinical and clinical study data suggest that subcutaneous administration of CBL-514 may be effective in reducing subcutaneous fat in humans. The pharmacological studies conducted by Caliway Biopharmaceuticals support the intended clinical dose and route of administration of the planned Phase 2 study (refer to further details in IB).

6.4. Dosage and Treatment Periods

The study is divided into 2 stages:

Stage 1

Stage 1 will include a total of 24 subjects enrolled in 4 sequential escalating CBL-514 dose groups and will receive a single course of CBL-514: 320 mg, 480 mg, 640 mg, and 800 mg. The groups will be open label. The 4 groups will each include 6 subjects.

Subjects in Group 1 (320 mg) will receive CBL-514 injections on thighs, with total allocated dose of IP evenly divided into 2 thighs. Subjects from Group 2 to 4 (480 mg-800 mg) will receive CBL-514 injections on abdomen with allocated dose of IP. The dosing scheme is presented in [Table 7](#).

Stage 2

In Stage 2 of the study, a total of 75 subjects will be randomized to 2:1 (i.e., 50 subjects in the CBL-514 group and 25 subjects in the placebo group). Each subject will receive up to 4 courses of CBL-514 or placebo. Each course of CBL-514/placebo will be administered 4 weeks apart, over a period of up to 12 weeks. Only a single dose level of CBL-514 will be administered in Stage 2, which will be set no higher than the highest safe dose from Stage 1 of the study.

6.4.1. Rationale for Dose Selection

The maximum dose of this Phase 2 study is estimated based on the 8-week repeated-dose GLP toxicity studies in Sprague-Dawley rats and Beagle dogs, respectively.

[REDACTED]

[REDACTED]

[REDACTED]

[REDACTED]

[REDACTED]

[REDACTED]

[REDACTED]

[REDACTED]

[REDACTED]

[REDACTED]

[REDACTED]

Furthermore, the completed Phase 1/2a Study (protocol number: CBL-16001) had evaluated the safety of CBL-514 injection for reducing abdominal subcutaneous fat. Single treatment of CBL-514 were administered with dose levels of 2 mg, 10 mg, 20 mg, 40 mg, 80 mg, 160 mg, 240 mg, and 320 mg per subject, which have shown overall favorable results in physical examination, vital signs, ECG, laboratory tests including biochemistry, hematology, coagulation, and urinalysis profiles.

There was no systemic TEAEs from CBL-514, the most frequent TEAEs were ISRs. During SAD progress, the severity and duration of common ISRs did not show apparent difference among cohorts, which provided even more evidence on the safety of CBL-514 in human.

Based on the nonclinical and clinical results above, the dose escalation groups in the present study are structured as 320 mg, 480 mg, 640 mg, and 800 mg to assess safety and tolerability of higher doses of CBL-514 when injected in abdominal or thigh adipose tissue.

The doses used in this study are 2 mg/cm², which are all within the pharmacologically active dose range. (Please refer to IB for more details) Moreover, the Phase 1 component of CBL-16001 study have assessed safety in human from 0.5 ~ 2 mg/cm² with favourable safety profiles. Based on the results of the CBL-16001 Phase 1 study, the incidence of TEAEs reported were similar across all dose cohorts especially in Cohort 5 to 9, where subjects received the same unit dose (2 mg/cm²) over an increasing treatment area/ total dose per Cohort. Therefore, CBL-0202 has adopted the similar design to have a consistent unit dose, 2 mg/cm², throughout the study. It is expected that the severity or incidence of adverse events in CBL-0202 study will not increase compared to the completed study, even though the dose used is higher.

The purpose of increasing the total dose in CBL-0202 study is to accommodate the larger treatment area needed to cater different needs of subjects due to various shape of abdomen/thighs and level of fat accumulation, so as to reach meaningful efficacy and to also improve on the overall appearance and shape to achieve aesthetically pleasing result for the subjects.

6.5. Subject Population

The study will be conducted in male and female subjects aged 18 to 64 years (inclusive at the time of informed consent) with

- thigh subcutaneous fat thickness of at least 1.00 cm (10.0 mm) and up to 4.00 cm (40.0 mm) measured by ultrasound at Screening and Day 1 for Group 1 in Stage 1,
- abdominal subcutaneous fat thickness of at least 2.00 cm (20.0 mm) and up to 5.00 cm (50.0 mm) measured by ultrasound at Screening and Day 1 for Group 2-4 in Stage 1,
- and abdominal skinfold thickness of at least 3.00 cm (30.0 mm) and up to 8.00 cm (80.0 mm) by pinch method (measured by calibrated caliper) at Screening for Stage 2.

Women of childbearing potential (WOCBP) will be included and are subject to contraceptive requirements during the study from Screening until study completion, including the follow-up period, and for at least 90 days after the last dose of IP (see [Section 9](#)). WOCBP must demonstrate negative pregnancy testing at Screening and before administration of IP. This is in line with regulatory Guidance on Nonclinical Safety Studies for the Conduct of Human Clinical Trials and Marketing Authorization for Pharmaceuticals (FDA 2006).

6.6. Ethical Principles

This study will be conducted in accordance with the principles of the current Declaration of Helsinki (Ethical Principles for Medical Research Involving Human Subjects). The conduct of the study will be in accordance with the International Conference for Harmonisation (ICH) Integrated Addendum to E6(R1): Guideline for ICH GCP E6(R2), annotated with comments by the Australian Therapeutic Goods Administration (TGA; 2018).

This study will be conducted under a protocol reviewed and approved by an IRB/IEC and investigations will be undertaken by scientifically and medically qualified persons; where the benefits of the study are in proportion to the risks.

7. TRIAL OBJECTIVES AND PURPOSE

7.1. Objectives

7.1.1. Primary Objectives

7.1.1.1. Stage 1

The primary objective of Stage 1 of the study is to:

- Evaluate the safety and tolerability of injection lipolysis with CBL-514

7.1.1.2. Stage 2

The primary objectives of Stage 2 of the study are to:

- Assess the proportion of subjects who lose at least 150 mL of subcutaneous fat volume as measured by ultrasound compared with placebo

7.1.2. Secondary Objectives

7.1.2.1. Stage 1

The secondary objectives of Stage 1 of the study are to:

- Assess the efficacy of single course of CBL-514 at applicable dose levels in reducing subcutaneous fat over the treated area as measured by ultrasound compared with Baseline.

*Note: no efficacy endpoints/objectives will be assessed for Group 1 of Stage 1 study.

7.1.2.2. Stage 2

The secondary objectives of Stage 2 of the study are to:

- Assess the proportion of subjects who lose at least 200 mL of subcutaneous fat volume as measured by ultrasound compared with placebo
- Evaluate the number of treatments required to first occurrence of reducing at least 150 mL of subcutaneous fat volume over the treated area as measured by ultrasound in CBL-514 group
- Assess the efficacy of up to 4 courses of CBL-514 in reducing subcutaneous fat volume over the treated area as measured by ultrasound compared with placebo
- Assess the efficacy of up to 4 courses of CBL-514 in reducing subcutaneous fat volume over the treated area as measured by ultrasound compared with Baseline
- Evaluate safety following up to 4 courses of CBL-514 when compared with placebo

7.2. Endpoints

7.2.1. Primary Endpoints

7.2.1.1. Stage 1

The primary endpoints of Stage 1 of the study are:

- Safety and tolerability following single dose of CBL-514 as assessed by recording of TEAEs, laboratory assessments, vital signs, ECGs, physical examinations, and injection site assessment.

7.2.1.2. Stage 2

The primary endpoints of Stage 2 of the study are:

- The proportion of subjects who lose at least 150 mL of subcutaneous fat as measured by ultrasound from Baseline to follow-up visits compared with placebo. [Time frame: Visit 2 (Baseline), Visit 6 and Visit 7]

7.2.2. Secondary Endpoints

7.2.2.1. Stage 1

The secondary endpoints of Stage 1 of the study are:

- Reduction of subcutaneous fat thickness as measured by ultrasound compared with Baseline. [Time frame: Day 1 and Week 4]
- Reduction of subcutaneous fat volume over the treated area as measured by ultrasound compared with Baseline. [Time frame: Day 1 and Week 4]

*Note: no efficacy endpoints/objectives will be assessed for Group 1 of Stage 1 study.

7.2.2.2. Stage 2

The secondary endpoints of Stage 2 of the study are:

- The proportion of subjects who lose at least 200 mL of subcutaneous fat as measured by ultrasound from Baseline to follow-up visits compared with placebo. [Time frame: Visit 2 (Baseline), Visit 6 and Visit 7]
- Number of treatments required to first occurrence of reducing at least 150 mL of subcutaneous fat volume over the treated area as measured by ultrasound in CBL-514 group [Time frame: from Visit 2 (Baseline) to Visit 7]
- Reduction of subcutaneous fat volume over the treated area as measured by ultrasound from Baseline to follow-up visits compared with placebo. [Time frame: Visit 2 (Baseline), Visit 6 and Visit 7]
- Reduction of subcutaneous fat volume over the treated area of the CBL-514 group as measured by ultrasound compared with individual Baseline. [Time frame: Visit 2 (Baseline), Visit 3, Visit 4, Visit 5, Visit 6, and Visit 7]

- Safety as assessed by recording of TEAEs, laboratory assessments, vital signs, ECGs, physical examinations, and ISRs compared with placebo

8. INVESTIGATIONAL PLAN

8.1. Overall Study Design

This is a 2-stage adaptive design, Phase 2 study to evaluate the efficacy, safety, and tolerability of CBL-514 injection for reducing abdominal or thigh subcutaneous fat. This Phase 2 study has an integrated design consisting of a SAD part in Stage 1. Stage 2 will be conducted as a single-blind, placebo-controlled study, with 1 treatment group and 1 placebo group. A total of approximately 99 adult subjects with

- thigh subcutaneous fat thickness of at least 1.00 cm (10.0 mm) and up to 4.00 cm (40.0 mm) measured by ultrasound at Screening and Day 1, for Group 1 in Stage 1,
- abdominal subcutaneous fat thickness of at least 2.00 cm (20.0 mm) and up to 5.00 cm (50.0 mm) measured by ultrasound at Screening and Day 1 for Group 2-4 in Stage 1,
- and abdominal skinfold thickness of at least 3.00 cm (30.0 mm) and up to 8.00 cm (80.0 mm) by pinch method (measured by calibrated caliper) at Screening for Stage 2,

will be enrolled across the 2 stages of the study.

Stage 1 (single dose, open label, dose escalation)

Stage 1 will include a total of 24 subjects enrolled in 4 sequential escalating CBL-514 dose groups and will receive a single course of CBL-514: 320 mg, 480 mg, 640 mg, and 800 mg. The groups will be open label. The 4 groups will each include 6 subjects.

Subjects in Group 1 (320 mg) will receive CBL-514 injections on thighs, with total allocated dose of IP evenly divided into 2 thighs. Subjects from Group 2 to 4 (480 mg-800 mg) will receive CBL-514 injections on abdomen with allocated dose of IP.

Based upon SRC recommendation intermediate doses may be explored.

The dosing scheme is presented in [Table 7](#).

A schematic of the study design is provided in [Figure 1](#). Local effects of CBL-514 injection will be evaluated, and blood samples will be taken and analyzed to assess the safety of IP.

Subjects will be screened for inclusion and exclusion criteria during a 28-day screening period (Day -28 to Day -1). At the Treatment visit (Day 1), eligible subjects will be sequentially assigned to receive 1 course of allocated CBL-514 dose.

Subjects will visit the site on each of the study visits. Subjects will remain onsite for observation for at least 1 hour after the administration of CBL-514, or longer at the discretion of the Investigator and until all planned assessments for the visit are completed.

Subjects who are withdrawn from the study earlier than planned should attend an ET visit as soon as possible after early withdrawal, no later than 6 weeks from the last dose received.

A subject diary will be provided to each subject, to record if there are any changes to the injection site/s or any discomforts from Day 1 until last clinic visit or when all ISRs have resolved or stabilized. Subjects will be instructed to bring the subject diary with them for all visits to the clinic.

During Stage 1 of the study, the SRC will meet after all subjects in a dose group have completed the Week 1 visit. The SRC will review all reported AEs, AESIs, laboratory trends, and vital signs of all subjects from each dose group. Based upon review of available safety and tolerability data from each preceding dose group, the SRC will make a decision on progressing to the next dose group.

The safety and tolerability data of CBL-514 from Stage 1 will be reviewed by the SRC before commencement of Stage 2 (see [Section 8.3](#)). A top-level summary of safety data will be submitted to the relevant IRB/IEC for review before proceeding to Stage 2 of the study.

Study visits and assessments for Stage 1 of the study will occur as delineated in the Schedule of Assessments ([Table 4](#)).

Stage 2 (multiple-dose, randomized, single-blind, parallel, placebo-controlled study)

Stage 2 will be conducted as a single-blind study, with 1 CBL-514 group and 1 placebo group. Each subject will receive up to 4 treatments of allocated CBL-514 (2 mg/cm²) or placebo administered on abdomen, once every 4 weeks. The minimum dose is 300 mg per treatment and the maximum dose is 600 mg per treatment. The dose adjustment will depend on the level of fat accumulation on subject's abdomen at the discretion of the Investigator.

Stage 2 of the study will be initiated after IRB/EC review of top-level summary of safety data from Stage 1 of the study. The dose for Stage 2 will be based on a review of the safety data from Stage 1 of the study and the dose for Stage 2 will be set no higher than the highest safe dose from Stage 1.

In Stage 2, subjects will be randomized 2:1 CBL-514 group vs placebo group. Considering drop-out rates, approximately 75 subjects will be enrolled (50 subjects in the CBL-514 group and 25 subjects in the placebo group) in order to have 56 evaluable subjects for the 2 groups.

Subjects should have sufficient subcutaneous fat on their abdomen to receive injections on Day 1. This will be based on eligibility criteria set out in [inclusion criterion 3](#). Before administration, the Investigator should evaluate whether a subject is able to receive the minimum dose, 300 mg (25 injections) as defined by Study Drug Administration Manual. [REDACTED]

[REDACTED] If a subject is not able to receive the minimum injection dose, the ongoing treatment and post-dose assessments will be cancelled and the remaining treatment visits would not be required for that subject. For subjects that do not complete 4 treatments due to not enough residual fat, the subject will be requested to continue with follow-up visits (Visit 6 and 7). This arrangement would not be regarded as missing protocol required visits, or as discontinuation from the study.

If a subject cannot complete the 4 treatments and withdraws from the study because of reasons except for dose adjustment, only the ET visit should be performed for final follow-up.

Subjects will be screened for inclusion and exclusion criteria during a 28-day screening period (Day -28 to Day -1). At Visit 2 (Day 1), eligible subjects will be randomized 2:1: (i.e., CBL-514 group: 50 subjects; placebo group: 25 subjects) to receive CBL-514 or placebo, respectively.

Subjects will visit the site on each of the study visits and will remain onsite for observation for 1 hour after the administration of the IP, or shorter/ longer at the discretion of the Investigator and until all planned assessments for the visit are completed.

An ET visit has been planned for subjects who are withdrawn from the study earlier than planned for assessment as soon as possible after early withdrawal, no later than 6 weeks from the last dose received.

A subject diary will be provided to each subject to record if there are any changes to the injection site/s or any discomforts in between visits. Subjects will be instructed to bring the subject diary with them for all visits to the clinic.

Study visits and assessments for Stage 2 of the study will occur as delineated in the Schedule of Assessments presented in [Table 5](#).

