 - ² Anthropometric parameters include body height, body weight and abdominal skinfold thickness measured by caliper. Body weight will be measured at all visits to calculate the BMI. Body height and abdominal skinfold thickness (by caliper) will be measured at Screening only.
 - ³ Ultrasound – Thickness of fat will be obtained by ultrasonic measurements across target area. Abdominal ultrasound will be performed within 4 days before Visit 2 (Day 1), Visits 3, 4 and 5; and 4 days before/after the follow-up visits.
 - ⁴ A complete physical examination will include, at a minimum, assessments of the cardiovascular, respiratory, gastrointestinal, and neurological systems and will be performed pre-dose.
 - ⁵ On Visit 2 (Day 1), Visit 3, Visit 4, and Visit 5, the injection site assessments will be performed pre-dose and post-dose. Subjects will document any change to the ISRs in between visits in the Subject Diaries.
 - ⁶ On Visit 2 (Day 1), Visit 3, Visit 4, and Visit 5, vital signs assessments to be performed pre-dose. Vital sign assessments include temperature, pulse rate, blood pressure, and respiratory rate.
 - ⁷ On Visit 2 (Day 1), ECG assessments will be performed pre-dose. ECG to be performed in supine position after at least 5 minutes rest. The following ECG parameters will be recorded: heart rate, RR interval, PR interval, QT interval, and QRS interval.
 - ⁸ Blood tests include biochemistry, hematology, and coagulation assessments. Biochemistry assessments include albumin, ALT, AST, ALP, triglyceride, total cholesterol, LDL-C, HDL-C, TBIL, GGT, urea, creatinine, eGFR, HbA1c, FBS, Sodium, Potassium, Bicarbonate, and Chloride. Hematological assessments include Hb, Hct, RBC count, mean corpuscular volume, WBC count, WBC differential, and platelet count. Coagulation assessments include aPTT, Prothrombin time, and INR.
 - ⁹ Urinary samples for dipstick will be collected.
 - ¹⁰ Serum β -hCG test will be taken for WOCBP at Screening visit only. FSH test is required for females who are post-menopausal at Screening visit. Urine β -hCG strip test will be taken for WOCBP for other scheduled visits.
 - ¹¹ Virology tests include HIV/HBV/HCV infection test. Active HIV infection is detected by detectable positive HIV Ag/Ab combo test; HBV: HBsAg; HCV: positive anti-HCV antibody.

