9. SELECTION AND WITHDRAWAL OF SUBJECTS

9.1. Subject Inclusion Criteria

To be eligible for this study, a subject must meet **all** of the following inclusion criteria:

1. Male or female, aged 18 years to 64 years old (at Screening), inclusive.
2. BMI > 18.5 and < 35 kg/m² and body weight ≥ 50 kg at Screening and Day 1.
3. Subject has subcutaneous fat thickness surrounding the center of localized area of treatment.
 - a. For Group 1 (320 mg) in Stage 1, thigh subcutaneous fat thickness of at least 1.00 cm (10.0 mm) and up to 4.00 cm (40.0 mm) measured by ultrasound at Screening and Day 1.
 - b. For Group 2-4 (480 mg-800 mg) in Stage 1, abdominal subcutaneous fat thickness of at least 2.00 cm (20.0 mm) and up to 5.00 cm (50.0 mm) measured by ultrasound at Screening and Day 1.
 - c. For Stage 2, abdominal skinfold thickness of at least 3.00 cm (30.0 mm) and up to 8.00 cm (80.0 mm) by pinch method (measured by calibrated caliper) at Screening.
4. Subject has stable body weight (identified as ≤ 5% weight change per subject report) for at least 3 months before Screening and during the study.
5. Subject who has maintained a stable lifestyle (e.g. exercise, eating patterns, and smoking habit) per subject report for at least 3 months before Screening and during the study.
6. Voluntarily signs the ICF and, in the opinion of the Investigator or delegate, is physically and mentally capable of participating in the study, and willing to adhere to study procedures.

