10.7. Blinding

Stage 2 of this study will be conducted in a single-blind manner where the subjects are blinded to treatment but the Investigator, site staff, and the Sponsor, including the Medical Monitor, will be unblinded to treatment assignment to assess safety on an ongoing basis.

Methods of blinding

- Due to the difference in appearance of the placebo and CBL-514, to keep the study single blind, the study needs to create visual barriers to blind subjects. Blinding for subjects will be maintained by physical barrier "sheet" placed over the chest obstructing the subjects own view of their abdomen, using a blindfold/sunglasses to cover subjects' eyes while administration takes place.

If during the study the blind is broken for any reason:

- The reason for unblinding is to be documented in the subject's source documents and case report forms (CRFs). Subjects that were unblinded for any reason during their participation in the study will not be replaced.
- As soon as possible, and without revealing the subject's study treatment assignment (unless important to the safety of participants remaining in the study), the Investigator must notify the Sponsor about unblinding and the reason for unblinding.

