12.2.2. Visit 2: Treatment/Baseline (Day 1)

12.2.2.1. Before Dosing

Prior to dosing on Day 1, subjects will be randomized to respective groups (i.e., CBL-514 group or placebo group) after confirmation of eligibility.

The following assessments will be carried out prior to the administration of IP unless otherwise noted³:

- Determine subject's eligibility based on inclusion/exclusion criteria
- Collect anthropometric parameters (including body weight)
- Perform abdominal ultrasound. Abdominal ultrasound may be performed up to 4 days before Day 1
- Perform medical examinations:
 - Physical examination⁴
 - Injection site assessment
 - Vital signs (body temperature, pulse rate, systolic and diastolic BP, and respiratory rate) evaluation⁴
 - ECG⁴
- Collect blood/urine to perform laboratory evaluations⁴:
 - Biochemistry panel
 - Hematology panel
 - Coagulation panel
 - Urinalysis
 - Pregnancy test for WOCBP (urine)
- Randomization
- Take photographs on the target abdominal area pre-dose.
- Before the administration of the injections,
 - Subjects will take an analgesic (pain killer) as recommended by the Investigator
 - Wipe subject's abdomen with an antiseptic solution
 - Apply local anesthesia used in local practice to the injection area

³ Available measurements of clinical evaluations (physical examinations, vital signs, and ECG) and laboratory evaluations (biochemistry, hematology, coagulation, and urinalysis) **within 14 days prior to CBL-514/Placebo dose** can be accepted as the Baseline value and will not necessitate duplicate examinations. If study drug dose is within 7 days of Screening pregnancy test, pregnancy test on Day 1 will not necessitate be necessary to assess.

In cases where more than 1 data is available for a certain evaluation, the latest value prior to the study drug administration will be used as the Baseline value.

⁴ Assessment/collection can be performed on or within 4-days window prior to visit date.

- A cold compress may also be applied before the injection(s) if needed

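### Stage 2: the check that a subject can take the minimum number of injections is not required before randomisation, so it may be made on Day 1 with the arm known

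*Protocol*

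**What the plan says.** Protocol 8.1 makes two statements about fat on the abdomen in Stage 2. The first concerns entry: "Subjects should have sufficient subcutaneous fat on their abdomen to receive injections on Day 1". The section leaves this to the third inclusion criterion. The second is a judgement about each treatment: "Before administration, the Investigator should evaluate whether a subject is able to receive the minimum dose, 300 mg (25 injections"). Sections 8.1 and 8.3 both say that if the answer is no, that treatment is cancelled and the remaining treatment visits are not required.

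Criterion 3c in 9.1 reads "For Stage 2, abdominal skinfold thickness of at least 3.00 cm (30.0 mm) and up to 8.00 cm (80.0 mm) by pinch method", with the reading taken at Screening. Footnote 2 of Table 5 confirms this: "Body height and abdominal skinfold thickness (by caliper) will be measured at Screening only".

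Section 12.2.2.1 sets out Visit 2: "Prior to dosing on Day 1, subjects will be randomized to respective groups" once eligibility has been confirmed. Its list of pre-dose steps includes Randomization, followed by photographs and preparation for the injections. The minimum-injection check is not in the list.

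Section 10.7 states that "the Investigator, site staff, and the Sponsor, including the Medical Monitor, will be unblinded to treatment assignment".

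Four rules decide what happens to a randomised subject who is never dosed:
- Protocol 16.1.1 limits the ITT population to subjects who received at least one course.
- SAP 4.1.1 keeps every randomised subject in the ITT population, dosed or not. Protocol Section 16 gives the SAP precedence.
- SAP 3.1 bases percentages on subjects with non-missing data unless stated otherwise, and Addendum 1.0 removed imputation.
- Protocol 9.5 replaces an enrolled but undosed subject with one who receives the same treatment.

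**The concern.** Whether a subject's abdomen can take the minimum number of injections decides whether that subject can be treated at all. It is in effect an entry condition, yet it is not written as one. A skinfold thickness measured up to 28 days earlier does not show whether 25 grid spaces can be placed, so the later judgement does the real work.

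That judgement is discretionary, and the person making it is unblinded once the subject is randomised. If it is made after allocation, a borderline subject could be judged able in one arm and unable in the other. The two arms would then no longer be the groups that randomisation created, and no later analysis can fully repair that.

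**Working it through.** **Check of the plan's own figures.** Minimum dose: 25 injections × 2.4 mL × 5 mg/mL = 300 mg, over 25 × 6 cm² = 150 cm². Evaluable subjects (synopsis Table S3, Protocol 10.4.1): 50 × (1 − 0.16) = 42 and 25 × (1 − 0.44) = 14, total 56. Both reproduce. The concern is about sequence, not about these numbers.

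**What must be done before randomisation.** Set side by side:

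| Item | In Stage 2 eligibility (9.1)? | In the Visit 2 list (12.2.2.1)? | Timing stated |
|---|---|---|---|
| Caliper skinfold, 3c | Yes | No new reading | Screening only |
| Abdominal ultrasound | No threshold for Stage 2 | Yes | Up to 4 days before Day 1 |
| Minimum-injection check | No | No | Before administration |
| Randomization | n/a | Yes | After eligibility, before dosing |

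Randomisation also precedes administration. A check tied only to administration can therefore fall on either side of randomisation, and nothing visible requires it to come first.

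**What happens to a Day 1 failure after allocation.**
- Protocol ITT: excluded, because no course was received.
- SAP ITT: included. The subject counts in the responder percentage only if there is a post-baseline ultrasound; otherwise the non-missing rule removes the subject and nothing is imputed.
- Per-protocol set: excluded, since the SAP builds it from a set that requires a course of treatment.
- Follow-up: Visit 6 is timed from the final treatment, which this subject never had. The cancellation rule in the synopsis and Table 5 names only Visits 3, 4 and 5.
- Replacement: same treatment. If the site knows that its next subject is the replacement, it knows that subject's arm before enrolling them.

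**Size.** The documents give no expected number of Day 1 failures. Each one is 1/25 = 4% of randomised placebo subjects or 1/50 = 2% of CBL-514 subjects (1/14 = 7.1% and 1/42 = 2.4% of the planned evaluable numbers). For an assumed range of 1 to 3 in one arm:
- Placebo: 4% to 3/25 = 12%.
- CBL-514: 2% to 3/50 = 6%.

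If they were not replaced, one loss per arm would leave 49 × 0.84 + 24 × 0.56 = 54.6 evaluable. Three losses in placebo alone would leave 50 × 0.84 + 22 × 0.56 = 54.3.

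For the effect on the primary proportion, assume 25 responders among 50 CBL-514 subjects (50.0%). If 1 or 3 undosed subjects leave the denominator instead of counting as non-responders, the rate becomes 25/49 = 51.0% or 25/47 = 53.2%.

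**The case against.** A reader might infer from the order of the steps in 12.2.2.1 that the check is designed to follow randomisation. The documents do not say so. The check is absent from that list, nothing states that the list is sequential, and the introduction to Section 12 orders assessments by invasiveness. Text next to the check is redacted, and the check is defined in a manual that is not supplied. Section 11.5 has the Investigator locate the Reference point at Screening, so some work on the treatment area precedes allocation. Eligibility is confirmed again on Day 1 before randomisation, and the synopsis words the stem of criterion 3 as requiring sufficient fat (9.1 omits that word). All of this stands: the order is unstated, and the sponsor may already control it elsewhere.

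The cancellation wording also points mainly to later visits. It speaks of residual fat, and the schedule names Visits 3, 4 and 5. Section 8.1 assigns Day 1 sufficiency separately, to criterion 3. This makes a Day 1 failure less likely to have been intended, but the check itself is not limited to later visits. Nor can it be said that a Day 1 failure has no follow-up: the request to attend Visits 6 and 7, both with ultrasound, could be read to cover it. What is missing is workable timing.

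Replacement under 9.5 would restore the number of subjects, so a permanent loss of 4% to 12% of the placebo arm should not be claimed. It would not restore an unpredictable allocation.

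**Conclusion.** The point holds as a gap in sequence. In Stage 2 the minimum-injection check is neither an eligibility criterion nor a required step before randomisation, and the person who makes it is unblinded. The plan as visible therefore permits a randomised subject to be left undosed on Day 1 by an arm-aware decision.

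The documents do not support the stronger conclusion that the check does fall after allocation, or that Investigators will exclude subjects by arm. The size is unknown: each case is 4% of placebo or 2% of CBL-514 subjects, and the range of 1 to 3 cases and the 25/50 response rate are assumptions for illustration. The likely effect is modest. It is still worth removing, because the comparison is small, the judgement is discretionary and the correction costs almost nothing.

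The conclusion assumes that neither the redacted text nor the Study Drug Administration Manual already places the check before randomisation. If one of them does, a cross-reference in 12.2.2.1 is enough.

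**What to change.** In 9.1 and 12.2.2.1, require the existing Day 1 check to be made and recorded before the Randomization step. A subject who fails it is a screen failure and is not randomised. Checks at Visits 3 to 5 stay as they are, and no dose or number of injections changes.

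Report any subject who is nevertheless randomised but undosed, by arm and with the reason. If enrolment has closed, this reporting is the part that can still be done.

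Repeating the caliper reading on Day 1 is not needed: skinfold thickness does not show whether the injections can be placed.

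The cost is amendment wording and one eCRF item. The downside is possibly a few screen failures on Day 1, in place of randomised subjects who are never treated.
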